3 STUDY SIZE

All the patients treated with this drug will be included in the all patient surveillance to be conducted for a specific period of time.

- Target number of cases: 600 cases
- Target number of cases observed: 300 cases treated for 12 weeks or longer (300 cases with Booklet 03 case report form)
(Cases who discontinued the drug before 12 weeks will also be included.)

[Rationale]

The incidence of all the adverse events included in the major investigation items of this study was 1.0% or higher in the drug group of the foreign phase 3 clinical study (304-WW Study). Assuming that the true incidence of an adverse event (particularly an adverse event included in the major investigation items) is 1.0%, 300 cases are required to observe at least 1 case with the event at a probability of at least 95%. The incidence of interstitial lung disease was 17.1% (14/82) in the multinational (Asian) phase 2 clinical study (2217-AP Study).

Assuming that the true incidence of interstitial lung disease is 17.1%, at least 40 cases with the disease can be observed at a probability of at least 95%.

Further, clinical study results showed that interstitial lung disease occurred on Week 4 after the start of the drug or later, and that, in rare cases, some adverse events had an increased incidence or delayed onset as the administration period was prolonged. Considering these results, it was decided to set a target that this study would include 300 cases treated with this drug for 12 weeks or longer.

Clinical study results showed that this drug could be continued for 12 weeks or longer in about 60% of the whole treated cases, with a discontinuance/drop-out rate at 12 weeks of about 40%. Considering that this study will be conducted under actual use condition, it is assumed that the discontinuance/drop-out rate at 12 weeks in this study will be increased by 10% to 50%. That is, it is assumed that this drug will be continued for 12 weeks or longer (the Booklet 03 case report form will be collected) in 50% of the cases included in this study.

Therefore, this surveillance was planned to register 600 cases to collect 300 cases treated with this drug for 12 weeks or longer. In addition, because cases which discontinue the drug before 12 weeks will be included in the study, the case report form will be collected from them to evaluate safety and effectiveness.

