# **6. ENDPOINTS AND COVARIATES**

## **6.1. Safety Endpoints**

1. *Onset state of adverse events/adverse reactions (particularly the major investigation items).*
2. *Onset state of adverse reactions and potential influencing factors (particularly the major investigation items).*
3. *Safety in patients with special background (pediatric patients, elderly patients, pregnant women, patients with renal or hepatic dysfunction).*
4. *Safety in patients with hepatic dysfunction (including the comparative examination with results from the foreign phase 1 clinical study).*
5. *Onset state of interstitial lung disease (including asymptomatic cases with imaging findings of the disease).*

6. *Potential risk factors of interstitial lung disease.*
7. *Characteristics of interstitial lung disease (imaging findings, onset timing, duration, and breakdown by severity).*
8. *List of clinical course of interstitial lung disease (contents of treatment, response to treatment, and outcome) and clinical course after the drug is restarted (presence/absence of recurrence/exacerbation, etc.).*
9. *Onset state of various related events suspected of causing interstitial lung disease (pneumonitis/lung infiltration and pulmonary fibrosis, etc.).*
10. Duration of treatment (Defined as the period from the date of initiation of treatment with this drug to the date of completion of treatment with this drug in this study. Patients for whom the completion of treatment is not reported in this study will be censored at the date of last dose.).

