- Platelet count  $\geq 100 \times 10^9/L$  ( $10 \times 10^4/\text{mm}^3$ ) [yes, no];
- Serum creatinine  $\leq 1.5$ -fold of institutional upper reference limit [yes, no];
- BUN  $\leq 1.5$ -fold of institutional upper reference limit [yes, no];
- Total bilirubin  $\leq 1.5$ -fold of institutional upper reference limit [yes, no];
- AST/ALT  $\leq 3$ -fold of institutional upper reference limit ( $\leq 5$ -fold of institutional upper reference limit if liver metastasis is observed) [yes, no];
- Chest CT normal [yes, no];
- Chest X-ray normal [yes, no];
- Measurement of markers for interstitial lung disease such as KL-6, normal [yes, no];
- Pulmonary function test (PFT) normal [yes, no];
- Measurement of oxygen saturation normal [yes, no];
- Total cholesterol  $\leq 350 \text{ mg/dL}$  ( $9.9 \text{ mmol/L}$ ) [yes, no];
- Triglyceride  $\leq 400 \text{ mg/dL}$  ( $4.56 \text{ mmol/L}$ ) [yes, no];
- Hemoglobin A1C  $< 10\%$  [yes, no];

- Fasting blood glucose  $\leq$ 1.5-fold of institutional upper reference limit [yes, no].

[Concomitant therapies and other background information]:

- Concomitant therapy (drug therapy) [absent, present];
- Concomitant therapy (non-drug therapy) [absent, present];
- History of smoking [absent, present];
- Family history of diabetes mellitus [absent, present];
- History of pulmonary surgery [absent, present];
- History of steroid use [absent, present];
- History of occupational and environmental exposure to asbestos, pneumoconiosis-producing dusts, etc. [absent, present];
- History of administration of highly concentrated oxygen for treatment of respiratory disease [absent, present];
- Drug allergies [absent, present];
- Allergies other than drug allergies [absent, present].

Corporate reference value

Test parameter	Unit	Lower limit		Upper limit	
		Male	Female	Male	Female
Hemoglobin	g/dL	13.5	11.3	17.6	15.2
White blood cell count	/ $\mu$ L	3900	3500	9800	9100
White blood cell differential/neutrophil	%	27	28	87	90
Platelet count	$\times 10^4/\mu$ L	13.1	13	36.2	36.9
AST	IU/L	7		38	

Test parameter	Unit	Lower limit		Upper limit	
		Male	Female	Male	Female
ALT	IU/L	4		44	
Total bilirubin	mg/dL	0.2		1	
Total cholesterol	mg/dL	130		219	
Triglyceride	mg/dL	30		150	
Fasting blood glucose	Mg/dL	60		110	
HbA1C	%	4.3		5.8	
BUN	mg/dL	8		20	
Serum creatinine	mg/dL	0.8	0.6	1.2	0.9
K	mEq/L	3.7		4.8	
P	mg/dL	2.5		4.5	
	mmol/L	0.8		1.4	
CRP	mg/dL			0.3	
SpO2	%	95		100	
KL-6	U/mL			500	
SP-D	ng/mL			<110	
SP-A	ng/mL	15		34.2	

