The number of patients with CTCAE Grade  $\geq 3$  adverse reactions and the incidence of CTCAE Grade  $\geq 3$  adverse reactions will be tabulated by SOC and PT by category shown below. •Further tabulation of serious adverse reactions” will be followed for categories.

- Seriousness;
- Known/unknown;
- Outcome;
- Timing of initial onset;
- Intervention;
- Administration of this drug;
- Duration of treatment;
- Total dose.

- **Further tabulation of adverse events**

The number of patients with adverse events and the incidence of adverse events will be tabulated by SOC and PT by category shown below. “• Further tabulation of serious adverse reactions” will be followed for categories.

- CTCAE Grade.

- **Further tabulation of unknown adverse reactions**

The number of patients with unknown adverse reactions and the incidence of unknown adverse reactions will be tabulated by SOC and PT by category shown below. “•Further tabulation of serious adverse reactions” will be followed for categories.

- Outcome.

- **Cumulative incidence of adverse reactions**

The cumulative incidence of adverse reactions will be graphically presented with the time to onset on the horizontal axis.

The cumulative incidence will be graphically presented in the same manner for interstitial lung disease, diabetes mellitus/hyperglycemia, hypercholesterolemia/hyperlipidemia, infection, mucositis-related adverse events, and skin disorder among major investigation items.

- **Cumulative incidence of CTCAE Grade  $\geq 3$  adverse reactions**

The cumulative incidence of CTCAE Grade  $\geq 3$  adverse reactions will be graphically presented with the time to onset on the horizontal axis.

The cumulative incidence will be graphically presented in the same manner for interstitial lung disease, diabetes mellitus/hyperglycemia, hypercholesterolemia/hyperlipidemia, infection, mucositis-related adverse events, and skin disorder among major investigation items.

- **Incidence of adverse reactions by patient demographic**

The number of patients with adverse reactions and the incidence of adverse reactions will be tabulated by item listed in “[Section 10.1.1. Patient demographics to be used to evaluate safety and efficacy.](#)”

Fisher’s exact test will be performed for nominal scale data and Cochran-Armitage test (exact method) for ordered scale data.

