**Nominal scale**

Item	Category	Remarks
AST/ALT $\leq$ 3-fold of institutional upper reference limit ( $\leq$ 5-fold of institutional upper reference limit if liver metastasis is observed)	Yes, No	
Chest CT normal	Yes, No	
Chest X-ray normal	Yes, No	
Measurement of markers for interstitial lung disease, such as KL-6, normal	Yes, No	
Pulmonary function test (PFT) normal	Yes, No	
Measurement of oxygen saturation normal	Yes, No	
Total cholesterol $\leq$ 350 mg/dL (9.9 mmol/L)	Yes, No	
Triglyceride $\leq$ 400 mg/dL (4.56 mmol/L)	Yes, No	
Hemoglobin A1C $<$ 10%	Yes, No	
Fasting blood glucose $\leq$ 1.5-fold of institutional upper reference limit	Yes, No	
Concomitant therapy (drug therapy)	Absent, Present	
Concomitant therapy (non-drug therapy)	Absent, Present	
History of smoking	Absent, Present	
Family history of diabetes mellitus	Absent, Present	
History of pulmonary surgery	Absent, Present	

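### In the visible SAP, baseline lung-marker, SpO2, glucose and lipid values are tested as risk factors only as yes/no proper-use items; graded versions, with KL-6, SP-D and SP-A separate, should be added beside them.

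*SAP*

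**What the plan says.** Protocol 6.4 lists SpO2, KL-6, SP-D, SP-A, total cholesterol, triglyceride, fasting blood sugar and HbA1c among the tests. The observation schedule in Protocol 6 places laboratory testing at the start of administration.

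SAP 8.2.5 turns these values into proper-use criteria, each answered yes or no. The lung-marker item reads "Measurement of markers for interstitial lung disease such as KL-6, normal [yes, no". SAP 10.1.1 repeats it in the nominal-scale table as "Measurement of markers for interstitial lung disease, such as KL-6, normal". SpO2 has its own normal/not normal item. The metabolic items are cut at HbA1c 10%, total cholesterol 350 mg/dL, triglyceride 400 mg/dL, and fasting glucose 1.5 times the institutional upper limit. None of the eight values appears in the ordered-scale table of 10.1.1. In 8.2.5 only age, height, weight and BMI are marked as continuous.

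SAP 8.2.6 tests the 10.1.1 factors: Fisher's "exact test will be performed for nominal scale data and Cochran-Armitage test (exact method) for ordered scale data". It then extends the tabulation to ILD, diabetes/hyperglycaemia, hypercholesterolaemia/hyperlipidaemia and three other major items. SAP 6.1 names "Potential risk factors of interstitial lung disease" as a safety endpoint, in line with Protocol objective 3.

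**The concern.** The baseline lung markers and SpO2 are direct candidates as risk factors for ILD, as are HbA1c and glucose for hyperglycaemia and lipids for hyperlipidaemia. The yes/no items are criteria for proper use of the drug. They were not chosen to describe how risk changes across the range of a marker.

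Two features reduce what the tests can show. First, the absolute metabolic cuts are far from the SAP's corporate upper limits, so a patient with HbA1c 9.5% is grouped with one at 5.0%, and few patients may fall on the other side. Second, one item for the lung markers cannot separate KL-6 from SP-D or SP-A, whatever the power.

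The SAP is more careful elsewhere. Age, body surface area, BMI, ECOG and Karnofsky status get ordered trend tests, and the efficacy section tabulates LDH at two cuts. At stake is how a null result on these factors is read: it could reflect the coding rather than the absence of an association.

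**Working it through.** **1. The plan's own figures.** Protocol 3 gives "Target number of cases: 600 cases" and "Target number of cases observed: 300 cases treated for 12 weeks or longer". Its rationale is that "300 cases are required to observe at least 1 case with the event at a probability of at least 95" percent, for a true rate of 1.0%. For ILD it states: "The incidence of interstitial lung disease was 17.1% (14/82) in the multinational (Asian) phase 2 clinical study (2217-AP Study".

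- P(at least 1 event) = 1 - 0.99^300 = 0.951.
- P(at least 40 ILD cases | n = 300, rate 17.1%) = 0.968 (binomial tail).
- 300 / (1 - 0.5) = 600 registered.

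All three reproduce. They concern seeing events; no power is stated for any factor test. With 600 patients about 600 × 0.171 = 103 ILD cases are expected.

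**2. How far the metabolic cuts lie from the SAP's corporate upper limits (8.2.5).**

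| Value | Proper-use cut | Corporate upper limit | Ratio |
|---|---|---|---|
| HbA1c (%) | 10 | 5.8 | 1.7 |
| Total cholesterol (mg/dL) | 350 | 219 | 1.6 |
| Triglyceride (mg/dL) | 400 | 150 | 2.7 |

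The lung items are different: they are cut at normal.

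**3. Information kept by a yes/no split.** For a normally distributed marker with a graded effect, a split that flags a share p keeps φ(z_p)² / [p(1 - p)] of the information, where z_p is the cut. For p = 0.5 this is 0.399² / 0.25 = 0.64.

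| Share flagged | 1% | 2% | 5% | 10% | 20% | 30% | 50% |
|---|---|---|---|---|---|---|---|
| Kept | 7% | 12% | 22% | 34% | 49% | 58% | 64% |
| Lost | 93% | 88% | 78% | 66% | 51% | 42% | 36% |

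**4. Power for ILD if the relation is graded.** Simulation: marker x standard normal, logit P(ILD) = a + b·x, overall rate 17.1%, two-sided 5%, complete baseline data. The odds ratios per SD are assumptions. The full-scale test on x is compared with Fisher's exact test on the flag.

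| N, OR per SD | Full scale | 50% flagged | 20% | 10% | 5% | 2% |
|---|---|---|---|---|---|---|
| 600, 1.35 | 80% | 58% | 52% | 39% | 30% | 21% |
| 600, 1.4 | 87% | 66% | 60% | 47% | 34% | 24% |
| 600, 1.5 | 95% | 81% | 74% | 64% | 48% | 34% |
| 600, 2.0 | 100% | 100% | 99-100% | 97% | 89% | 70% |
| 300, 1.35 | 48% | 30% | 27% | 22-23% | 20-21% | 10% |

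Repeat simulations at OR 1.4 agree to within about 3 points. At N = 600 and OR 1.4, a trend test on baseline quartiles has about 81%.

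**5. One flag shared by three lung markers.** Assume the flag is abnormal if any marker is, each is abnormal in 10-20% of patients, and only one is prognostic. At N = 600 and OR 1.35, power is 16-17% if the markers are uncorrelated and 34-39% if the correlation is 0.5, against 80% for the prognostic marker tested alone on its full scale.

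**6. The opposite case.** Suppose risk is flat and then steps up at the cut (OR 2.5, N = 600, 17.1% events). With 10% flagged, Fisher on the flag has about 80%, the full-scale test about 44% and the quartile trend about 28%. With 20% flagged, Fisher has 94% and the full-scale test 77%.

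**The case against.** The strongest reply has five parts.

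- **The graded model favours the full-scale test.** This is right. Step 6 shows the ranking reverses when risk steps up at the cut, so the yes/no tests must not be dropped.
- **A reader might infer that most of the power is lost.** The documents do not support that. They give neither the share flagged nor an effect size. In step 4, more than half the power goes only when about 10% or fewer are flagged, and at OR 2.0 even 10% flagged costs only 3 points. A loss of most of the information is plausible for HbA1c and lipids if only 1-5% exceed those cuts, and a loss of most of the power is plausible for the shared lung flag. Neither is established. The lung items are cut at normal, so the extreme-cut argument does not apply to them. No hyperglycaemia or hyperlipidaemia rate is given, so the power figures are for ILD only.
- **A reader might infer that no graded analysis is planned.** That cannot be said. Text directly after the major-item tabulations in SAP 8.2.6 is blacked out, and the amendment log says an analysis plan was moved into 8.2.6 and 8.2.7.
- **Related factors are tested.** Past and comorbid lung disease, ILD and diabetes, family history of diabetes, and normal CT, X-ray and pulmonary function are all in 10.1.1. They give partial cover but do not replace the marker values. Re-tabulating with corporate reference values does not help either: reference-based items stay binary, and the HbA1c and lipid cuts are absolute.
- **The study is not confirmatory, and testing the proper-use criteria serves its purpose.** True, and this argues for adding graded tests rather than replacing the existing ones.

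Two points are inferences: that the values are recorded as numbers (from the test list and the units in the reference table; the form fields are not shown), and that the lung item covers SP-D and SP-A (it names only KL-6 as an example).

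**Conclusion.** The point holds for the visible plan. Eight baseline values tied to named objectives enter the factor tests only as yes/no items, and KL-6, SP-D and SP-A have no items of their own. Under a graded relation the loss is roughly 35% to 90% of the information. For ILD at N = 600 and OR 1.4 per SD, power drops from about 87% to 60-66% with 20-50% flagged and to 24-47% with 2-10% flagged.

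This rests on a normal marker, a log-linear effect, complete baseline data and an assumed effect size. Patients without a measurement would lower both powers. Under a step at the cut the existing tests do better. What does not depend on these assumptions is that a single lung-marker item cannot identify which marker is associated with ILD. The change is worth making because it draws on tests the protocol already schedules, but it does not invalidate the planned tables.

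**What to change.** Keep the yes/no items in SAP 10.1.1 and their tests. Add to the ordered-scale table, for the factor tests in 8.2.6:

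- **ILD:** baseline KL-6, SP-D, SP-A and SpO2 as four separate items.
- **Diabetes/hyperglycaemia:** baseline HbA1c and fasting glucose.
- **Hypercholesterolaemia/hyperlipidaemia:** baseline total cholesterol and triglyceride.

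Baseline quartiles with the exact Cochran-Armitage test need no new method and no linearity assumption on the original scale. SpO2, with a corporate range of only 95-100%, may need fixed categories instead. The alternative is a univariable logistic model on the log value, reporting the odds ratio per doubling or per SD with its 95% confidence interval, at the price of a linearity assumption. State which markers the combined lung item covers, and report the share flagged and the number with a baseline value for each item.

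The cost is SAP wording and about eight more exploratory tests at an unadjusted 5%, on an already long factor list. Patients without a baseline value drop out of the added analysis. If the blacked-out text already contains it, a cross-reference from 10.1.1 is enough.

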### **8.2.6. Safety Analysis**

- **Incidences of adverse reactions and adverse events**

The number of patients with adverse reactions, serious adverse reactions, adverse events, serious adverse events, and Common Terminology Criteria for Adverse Events (CTCAE) Grade  $\geq 3$  adverse reactions and the incidences of these events will be calculated by system organ class (SOC) and preferred term (PT).

In addition, the number of patients with adverse reactions and the incidence of adverse reactions by inclusion/exclusion from the safety analysis set will be tabulated by SOC and PT in patients for whom the case report form was collected.

- **Further tabulation of adverse reactions**

The number of patients with adverse reactions and the incidence of adverse reactions will be tabulated by SOC and PT by category shown below.

- Seriousness [serious, non-serious];
- Known/unknown [known, unknown];
- Outcome [resolved/recovered, recovering, recovered with sequelae, not recovered];
- Timing of initial onset [ $>0$  to  $\leq 8$  weeks,  $>8$  to  $\leq 16$  weeks,  $>16$  to  $\leq 24$  weeks,  $>24$  to  $\leq 48$  weeks,  $>48$  to  $\leq 72$  weeks,  $>72$  to  $\leq 96$  weeks,  $>96$  weeks];
- Intervention [absent, present];
- Administration of this drug [no change in dose, temporary discontinuation, dose reduction, dose increase, discontinuation];
- Duration of treatment [ $>0$  to  $\leq 8$  weeks,  $>8$  to  $\leq 16$  weeks,  $>16$  to  $\leq 24$  weeks,  $>24$  to  $\leq 48$  weeks,  $>48$  to  $\leq 72$  weeks,  $>72$  to  $\leq 96$  weeks,  $>96$  weeks];
- Total dose [ $>0$  to  $\leq 200$  mg,  $>200$  to  $\leq 400$  mg,  $>400$  to  $\leq 600$  mg,  $>600$  to  $\leq 1200$  mg,  $>1200$  to  $\leq 1800$  mg,  $>1800$  to  $\leq 2400$  mg,  $>2400$  mg];
- CTCAE Grade[Grade 1,Grade 2,Grade 3,Grade 4,Grade 5].

- **Further tabulation of serious adverse reactions**

The number of patients with serious adverse reactions and the incidence of serious adverse reactions will be tabulated by SOC and PT by category shown below. “•Further tabulation of serious adverse reactions” will be followed for categories.

- Known/unknown;
- Outcome;

- Timing of initial onset;
- Intervention;
- Administration of this drug;
- Duration of treatment;
- Total dose;
- CTCAE Grade.

- **Further tabulation of CTCAE Grade  $\geq 3$  adverse reactions**

The number of patients with CTCAE Grade  $\geq 3$  adverse reactions and the incidence of CTCAE Grade  $\geq 3$  adverse reactions will be tabulated by SOC and PT by category shown below. •Further tabulation of serious adverse reactions” will be followed for categories.

- Seriousness;
- Known/unknown;
- Outcome;
- Timing of initial onset;
- Intervention;
- Administration of this drug;
- Duration of treatment;
- Total dose.

- **Further tabulation of adverse events**

The number of patients with adverse events and the incidence of adverse events will be tabulated by SOC and PT by category shown below. “• Further tabulation of serious adverse reactions” will be followed for categories.

- CTCAE Grade.

- **Further tabulation of unknown adverse reactions**

The number of patients with unknown adverse reactions and the incidence of unknown adverse reactions will be tabulated by SOC and PT by category shown below. “•Further tabulation of serious adverse reactions” will be followed for categories.

- Outcome.

- **Cumulative incidence of adverse reactions**

The cumulative incidence of adverse reactions will be graphically presented with the time to onset on the horizontal axis.

The cumulative incidence will be graphically presented in the same manner for interstitial lung disease, diabetes mellitus/hyperglycemia, hypercholesterolemia/hyperlipidemia, infection, mucositis-related adverse events, and skin disorder among major investigation items.

- **Cumulative incidence of CTCAE Grade  $\geq 3$  adverse reactions**

The cumulative incidence of CTCAE Grade  $\geq 3$  adverse reactions will be graphically presented with the time to onset on the horizontal axis.

The cumulative incidence will be graphically presented in the same manner for interstitial lung disease, diabetes mellitus/hyperglycemia, hypercholesterolemia/hyperlipidemia, infection, mucositis-related adverse events, and skin disorder among major investigation items.

- **Incidence of adverse reactions by patient demographic**

The number of patients with adverse reactions and the incidence of adverse reactions will be tabulated by item listed in “[Section 10.1.1. Patient demographics to be used to evaluate safety and efficacy.](#)”

Fisher’s exact test will be performed for nominal scale data and Cochran-Armitage test (exact method) for ordered scale data.

Tabulation will be performed in the same manner for interstitial lung disease, diabetes mellitus/hyperglycemia, hypercholesterolemia/hyperlipidemia, infection, mucositis-related adverse events, and skin disorder among major investigation items.

For items using reference laboratory test values, results using corporate reference values will be tabulated in addition to results using institutional reference values.

- **Incidence of CTCAE Grade  $\geq 3$  adverse reactions by patient demographic**

The number of patients with CTCAE Grade  $\geq 3$  adverse reactions and the incidence of CTCAE Grade  $\geq 3$  adverse reactions will be tabulated by item listed in “[Section 10.1.1. Patient demographics to be used to evaluate safety and efficacy.](#)”

Tabulation will be performed in the same manner for interstitial lung disease, diabetes mellitus/hyperglycemia, hypercholesterolemia/hyperlipidemia, infection, mucositis-related adverse events, and skin disorder among major investigation items.

For items using reference values, results using corporate reference values will be tabulated in addition to results using institutional reference values.

- **Incidence of adverse reactions by medical history, prior treatment history, and concomitant therapy**

The number of patients with adverse reactions and the incidence of adverse reactions will be tabulated by category shown below.

The number of patients and incidence will be tabulated in the same manner for interstitial lung disease among major investigation items.

- Past medical history;
- Complications;
- Prior medications.

- **Incidence of CTCAE Grade  $\geq 3$  adverse reactions by medical history, prior treatment history, and concomitant therapy**

The number of patients with CTCAE Grade  $\geq 3$  adverse reactions and the incidence of CTCAE Grade  $\geq 3$  adverse reactions will be tabulated by category shown below.

- Past medical history;
- Complications;

- Concomitant medications;
- Non-drug therapies;
- Prior medications.
- **Subgroups**

Safety in the following subgroups will be analyzed.

1. Children (<15 years), adults ( $\geq 15$  years).
2. Elderly ( $\geq 65$  years), non-elderly (<65 years).
3. Presence or absence of pregnancy.
4. Presence or absence of hepatic dysfunction.
5. Presence or absence of renal dysfunction.
6. By indication.
7. By whether criteria for proper use are met.
8. History of hepatitis B, tuberculosis, and herpes zoster.
9. Severity of hepatic dysfunction.
10. Sex.
11. Complications.

The number of patients with adverse reactions, serious adverse reactions, and CTCAE Grade  $\geq 3$  adverse reactions and the incidence of these adverse reactions will be calculated by SOC and PT.

For items using reference values, results using corporate reference values will be tabulated in addition to results using institutional reference values.

- **Major investigation items**

The number of patients with adverse reactions falling under major investigation items and the incidence of these adverse reactions will be calculated by SOC and PT. The number of patients with adverse events and the incidence of adverse events will be tabulated in the same manner.

The same tabulation will be performed for each of the following items.

1. Interstitial lung disease.
2. A wide range of related events suspected of interstitial lung disease.
3. Dyspnea.
4. Diabetes mellitus/hyperglycemia.
5. Hypersensitivity reaction.
6. Diarrhea.
7. Hypophosphatemia.
8. Hypokalemia.
9. hypercholesterolemia/hyperlipidemia.
10. Infection.
11. Intracerebral hemorrhage.
12. Abnormality in wound healing.
13. Mucositis-related adverse events.
14. Skin disorder.
15. Acute renal failure.
16. Gastrointestinal perforation.

- **Further tabulation of interstitial lung disease**

The number of patients with adverse reactions and adverse events of interstitial lung disease and the incidences of these adverse reactions and adverse events will be tabulated by presence or absence of past or present history of lung disease and presence or absence of abnormal imaging findings at the initiation of treatment by category shown below.

- Seriousness;
- Clinical symptoms;
- Severity (CTCAE Grade);
- Time from the initiation of treatment to initial onset (weeks);
- Cumulative duration (weeks);
- Imaging findings suspected of interstitial lung disease.

The worst CTCAE Grade and treatment effect will be tabulated by presence or absence of treatment of interstitial lung disease.

The outcome in patients in whom interstitial lung disease was CTCAE Grade 1 at onset will be tabulated by status (continued/discontinued) of treatment.

The list of the course of interstitial lung disease and the list of the time course of CTCAE Grade will be prepared.

Graphs of time from the initiation of treatment to initial onset (weeks), outcome, and administration of this drug will be prepared by CTCAE Grade at onset. Graphs will be prepared in the same manner by maximum CTCAE Grade.

- **Further tabulation of diabetes mellitus/hyperglycemia**

The number of patients with adverse reactions of diabetes mellitus/hyperglycemia and the incidence of these adverse reactions will be tabulated by category shown below.

- Seriousness;
- Clinical symptoms;

- Severity (CTCAE Grade);
- Time from the initiation of treatment to initial onset (weeks);
- Cumulative duration (weeks);

Graphs of time from the initiation of treatment to initial onset (weeks) and outcome will be prepared by CTCAE Grade at onset.

- **Further tabulation of hypercholesterolemia/hyperlipidemia**

The number of patients with adverse reactions of hypercholesterolemia/hyperlipidemia and the incidence of these adverse reactions will be tabulated by category shown below.

- Seriousness;
- Clinical symptoms;
- Severity (CTCAE Grade);
- Time from the initiation of treatment to initial onset (weeks);
- Cumulative duration (weeks).

Graphs of time from the initiation of treatment to initial onset (weeks) and outcome will be prepared by CTCAE Grade at onset.

- **Further tabulation of infection**

The number of patients with adverse reactions of infection and the incidence of these adverse reactions will be tabulated by category shown below.

- Seriousness;
- Clinical symptoms;
- Severity (CTCAE Grade);
- Time from the initiation of treatment to initial onset (weeks);
- Cumulative duration (weeks).

Graphs of time from the initiation of treatment to initial onset (weeks) and outcome will be prepared by CTCAE Grade at onset.

- **Further tabulation of mucositis-related adverse events**

The number of patients with mucositis-related adverse reactions and the incidence of these adverse reactions will be tabulated by category shown below.

- Seriousness;
- Clinical symptoms;
- Severity (CTCAE Grade);
- Time from the initiation of treatment to initial onset (weeks);
- Cumulative duration (weeks).

Graphs of time from the initiation of treatment to initial onset (weeks) and outcome will be prepared by CTCAE Grade at onset.

- **Further tabulation of skin disorder**

The number of patients with adverse reactions of skin disorder and the incidence of these adverse reactions will be tabulated by category shown below.

- Seriousness;
- Clinical symptoms;
- Severity (CTCAE Grade);
- Time from the initiation of treatment to initial onset (weeks);
- Cumulative duration (weeks).

Graphs of time from the initiation of treatment to initial onset (weeks) and outcome will be prepared by CTCAE Grade at onset.

C [REDACTED]  
C [REDACTED]  
I [REDACTED]  
[REDACTED]

CCI

